6.3 Trial interventions

Eligible patients will be randomized to either a restrictive or a liberal RBC transfusion strategy. Hemoglobin will be checked minimally daily while on protocol up to and including Day 10 post aSAH or while in an ICU/HAU (high-acuity unit), and then at the discretion of the primary clinical team.

Restrictive RBC Transfusion Strategy: For patients randomized to this group, an RBC transfusion is permitted once a hemoglobin level of ≤ 80 g/L is observed over the first 21 days following aSAH. RBC transfusion will not be mandatory under this threshold, rather “usual care” will prevail, with the decision and timing of transfusion left to the discretion of the treating team.

Liberal RBC Transfusion Strategy: An RBC transfusion will be triggered by a hemoglobin level of ≤ 100 g/L over the first 21 days in hospital following aSAH.

Both Groups: All RBC transfusion orders will be a single unit unless the patient has active blood loss associated with hemodynamic instability (see section 9.1). In stable non-bleeding patients, a second unit of RBCs should only be given if a measured post-transfusion hemoglobin level remains below the patient’s assigned threshold. Protocol adherence and violations are discussed in section 9.1.

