2) Adherence to transfusion protocol (timely transfusion): As in the pilot, we endeavor not to exceed 6 hours from transfusion threshold event to transfusion initiation, in keeping with revascularization time performance measures in stroke literature^{70,71}. Transfusion protocol adherence is thus defined as an RBC transfusion initiated within 6 hours of threshold crossing, or Randomization. Non-adherence will be considered to have occurred if there is a delay of more than six hours between transfusion threshold event and transfusion initiation. Transfusions occurring more than 6 hours but within 24 hours will be considered a protocol deviation. A violation is a transfusion initiated greater than 24 hours from the threshold event. We will document reasons for non-adherence in the study case report form.

To improve protocol compliance and awareness we have involved neurosurgeons, interventionalists, transfusion medicine and intensivists at each study site. We will provide on-call house staff and clinicians end-of-the-day and start-of-the-weekend reminders about the study, both for future recruitable patients and enrolled patients. Reminders in the form of stickers and flagged pages will mark enrolled patients' medical record. A list of randomized patients will be kept in the transfusion medicine lab to allow for a secondary check of protocol adherence for when RBC transfusion is ordered. We will monitor daily hemoglobin measures to ensure compliance of transfusion within 6-hour target of meeting the threshold.

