1.2 Objectives

Our primary objective:

To evaluate the effect of a liberal (Hb trigger $\leq 100\text{g/L}$) versus a restrictive (Hb trigger $\leq 80\text{g/L}$) RBC transfusion strategy in acute aSAH patients with anemia ($\text{Hb} \leq 100\text{g/L}$) on patient-oriented functional neurologic outcome at 12 months.

Our secondary objectives:

To evaluate the effect of a liberal versus a restrictive RBC transfusion strategy on: a) 12-month overall function; b) quality of life at 12 months; c) mortality; d) delayed cerebral ischemia and radiographic vasospasm and e) clinically relevant stroke at hospital discharge on routine brain imaging.

Our tertiary objectives:

To evaluate the effect of a liberal versus a restrictive RBC transfusion strategy on lowest daily hemoglobin levels, RBC transfusions, expected and transfusion-related adverse events, mechanical ventilation and ICU and hospital length of stay.

Section 2: Study Methods

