2.1 Trial Design

SAHaRA is a multicenter pragmatic randomized trial in patients with aSAH that compares the effect of a liberal to a restrictive RBC transfusion strategy on the combined rate of death and severe disability at 12 months. Our PROBE (prospective, open-label, blinded endpoint) approach has been informed by and tested in our CIHR/CBS-funded pilot RCT.¹⁴

Trial interventions

Eligible patients are randomized to either a restrictive or a liberal RBC transfusion strategy. Hemoglobin is checked at least daily while on protocol up to and including Day 10 post aSAH or while in an ICU/HAU (high-acuity unit), and then at the discretion of the primary clinical team.

Restrictive RBC Transfusion Strategy: For patients randomized to this group, an RBC transfusion is permitted once a hemoglobin level of ≤ 80 g/L is observed over the first 21 days following aSAH. RBC transfusion below the threshold is not mandatory, rather “usual care” prevails, with the decision and timing of transfusion left to the discretion of the treating team.

Liberal RBC Transfusion Strategy: An RBC transfusion is triggered by a hemoglobin level of ≤ 100 g/L over the first 21 days in hospital following aSAH. Transfusion in this arm is mandatory.

Both Groups: All RBC transfusion orders are single unit unless the patient has active blood loss associated with hemodynamic instability (see section 9.1 of the protocol – see Appendix). In stable non-bleeding patients, a second unit of RBCs is given if a measured post-transfusion hemoglobin level remains below the patient’s assigned threshold. Protocol adherence and violations are discussed in section 9.1 of the protocol (see Appendix).

Duration of the intervention

The allocated transfusion strategy is applied from the time of randomization to 21 days after the original bleed, death or hospital discharge, whichever comes first. The first 21 days following aSAH represent the period of greatest vulnerability to the direct consequences of aSAH, and the sequelae, including DCI, that follow.

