Secondary Outcomes:

- The Functional Independence Measure as well as Motor and Cognition sub-scores will be analysed using a linear GLMM with an identity link function. The treatment effect will be reported as a mean difference with 95% CIs. In addition, the same analyses will be done however now excluding patients who are deceased.
- EQ-5D-5L Visual Analogue Scale will be analysed using a linear GLMM with an identity link function. The treatment effect will be report as a mean difference with 95% CIs. In addition, the same analyses will be done however now excluding patients who are deceased.
- Mortality in hospital will be analysed using a log-binomial GLMM and reported as a risk ratio with 95% CI.
- Mortality at 12 months will be analysed using a log-binomial GLMM and reported as a risk ratio with 95% CI.
- The number of patients with new cerebral infarction, DCI, and radiographic vasospasm, post randomization will be analysed using a log-binomial GLMM and reported as a risk ratio with 95% CI.

Tertiary Outcomes:

- Lowest daily hemoglobin level over the first 21 days in hospital will be presented graphically as means with 95% confidence intervals per group

- Proportion of patients receiving RBC transfusion with between group differences analysed using using a log-binomial GLMM
- Median number of RBC units transfused will be reported with interquartile ranges and presented as median difference with 95% CI using quantile regression analyses adjusting for site and sex.
- Proportion of patients with expected and transfusion-related adverse events will be reported with between group differences analysed using using a log-binomial GLMM adjusting for site and sex
- Duration of invasive mechanical ventilation will be reported as presented as median difference with 95% CI using quantile regression analyses adjusting for site and sex.
- ICU and Hospital Length of stay will also be described as medians with interquartile ranges and presented as median differences with 95% CI using quantile regression analyses adjusting for site and sex.

Pre-planned Subgroup Analyses:

We plan exploratory subgroup analyses for the primary outcome (as described above) in the following groups:

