Mortality – hospital	
 log-binomial GLMM and reported as a risk ratio with 95% CI 	-	
 Unadjusted model 	
 Centre Sex
Mortality – 12 months	
 log-binomial GLMM and reported as a risk ratio with 95% CI 	-	
 Unadjusted model 	
 Centre Sex
New cerebral infarction	
 log-binomial GLMM and reported as a risk ratio with 95% CI 	-	
 Unadjusted model 	
 Centre Sex
New DCI	
 log-binomial GLMM and reported as a risk ratio with 95% CI 	-	
 Unadjusted model 	
 Centre Sex
New radiographic vasospasm	
 log-binomial GLMM and reported as a risk ratio with 95% CI 	-	
 Unadjusted model 	
 Centre Sex
Tertiary Outcomes:				
Lowest daily hemoglobin	
 Presented graphically with 95% CI, per group 	-	-	-
Proportion of patients, per group, receiving RBC transfusion	
 Log-binomial GLMM 	-	
 Unadjusted model 	
 Centre Sex
Number of RBC units transfused	
 Presented as median difference with 95% CI using quantile regression 	-	
 Median with IQR 	
 Centre Sex

Expected and transfusion-related adverse events	
 • Log-binomial GLMM 	-	
 • Median with IQR 	
 • Centre • Sex
Duration of mechanical ventilation	
 • Presented as median difference with 95% CI using quantile regression 	-	
 • Median with IQR 	
 • Centre • Sex
Length of stay in the ICU and hospital	
 • Presented as median difference with 95% CI using quantile regression 	-	
 • Median with IQR 	
 • Centre • Sex

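### Lowest daily hemoglobin is plotted by arm with no between-arm estimate, and after day 10 the plotted means rest on discretionary sampling

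*SAP*

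**What the plan says.** SAP 1.2 words the tertiary objective as a comparison: "To evaluate the effect of a liberal versus a restrictive RBC transfusion strategy on lowest daily hemoglobin levels". For that outcome SAP 5.2 (Tertiary Outcomes) plans only this: "Lowest daily hemoglobin level over the first 21 days in hospital will be presented graphically as means with 95% confidence intervals per group". The corresponding row of SAP Table 4 reads "Presented graphically with 95% CI, per group", with a dash under sensitivity analyses, additional analyses and adjustments.

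On measurement, SAP 2.1 states: "Hemoglobin is checked at least daily while on protocol up to and including Day 10 post aSAH or while in an ICU/HAU", "and then at the discretion of the primary clinical team". Protocol 6.3 has the same rule. The allocated strategy is "applied from the time of randomization to 21 days after the original bleed, death or hospital discharge, whichever comes first", and the outcome covers the first 21 days in hospital (SAP 2.6 and 5.1).

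The protocol abstract lists lowest daily hemoglobin among the secondary outcomes. Protocol 6.10 says secondary outcomes will be assessed by multivariable linear or logistic regression. SAP 5.3 does not impute missing outcomes but says missing data will be reported with their frequencies. SAP 3.1 reserves p-values for the primary outcome.

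**The concern.** There are two linked problems.

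First, the objective asks for an effect of strategy and the analysis does not estimate one. Two means with separate intervals show a separation, but the reader has to subtract by eye and gets no interval for the difference.

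Second, the outcome window is longer than the window of mandated sampling. From day 11, a patient outside ICU/HAU has a value only if the treating team, which knows the allocation, orders one. With no imputation and no model, the plotted mean for such a day can only average those who were sampled. The SAP does not say so in words, but no other reading fits the dashes in Table 4 together with SAP 5.3.

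Hemoglobin separation is the direct evidence that the two strategies produced different exposures, and a reader would want it when interpreting a null primary result. If the late part of the curve mixes a treatment effect with a sampling effect, nothing planned would show which is which.

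**Working it through.** **Design figure.** The only one is the sample size of 740 for the primary outcome; the documents give no SD, expected difference or sample size for hemoglobin. With 40% versus 30%, two-sided 5% and 80% power: n per arm = [1.96·√(2·0.35·0.65) + 0.8416·√(0.24 + 0.21)]² / 0.10² = 355.9, so 356 per arm and 712 in total. Then 712/0.97 = 734.02, rounded up to 735, against the stated 740. The figure reproduces and this point does not touch it.

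**Objective against analysis.** In Table 4, lowest daily hemoglobin is the only row with a dash in every column after the main analysis. Each other tertiary row names a log-binomial GLMM or a median difference from quantile regression, adjusted for centre and sex. SAP 5.2 makes a GLMM the default for parametric analyses unless stated otherwise, and for this outcome it states otherwise.

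**What separate intervals omit.** For one day with n per arm and common SD, each arm's 95% half-width is 1.96·SD/√n and that of the difference is 1.96·SD·√(2/n). The SD is an assumption.
- n = 740·0.97/2 ≈ 359, SD 10 g/L: 1.03 per arm and 1.46 for the difference. Requiring the two intervals not to overlap demands a gap of 2 × 1.03 = 2.06, not 1.46.
- n = 75 (an assumed late-day count), SD 10: 2.26 per arm and 3.20 for the difference.
- For SD 8 to 15, the half-width of the difference runs from 1.17 to 2.19 at n = 359 and from 2.56 to 4.80 at n = 75.

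**To day 10.** Sampling is mandated at least daily for every patient on protocol, and the stated outcome is the daily minimum. The difference between the plotted means therefore estimates the stated outcome without a sampling distortion.

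**Days 11–21.** The documents give no hemoglobin SD, ICU/HAU stay or sampling fraction, so any distortion can only be illustrated. Assume a true gap of 15 g/L (restrictive mean 90, liberal 105), between-patient SD 7 and within-patient SD 5, so total SD √(49 + 25) = 8.6.

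(a) A simulation with 30–70% still in ICU/HAU:
- Sampling unrelated to hemoglobin: the gap reads 15.0 to 15.1.
- Sampling favours patients who are low relative to their own arm, equally in both arms: each mean is 1.2 to 2.2 g/L too low, but the gap stays at 15.0.
- Sampling is linked to hemoglobin in one arm only, or is more frequent in one arm: the gap reads 13.3 to 17.5.

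(b) One absolute rule for both arms: sampling probability 0.90 below a cut-point c and 0.25 above it. With z = (c − μ)/8.6, the sampled fraction is f = 0.25 + 0.65·Φ(z) and the sampled mean is μ − 8.6·0.65·φ(z)/f.
- c = 90: liberal z = −1.744, f = 0.28, mean 103.2; restrictive z = 0, f = 0.57, mean 86.1. The gap is 17.1.
- c = 100: liberal mean 100.6, restrictive 88.6. The gap is 12.0.
- c = 85: liberal mean 104.4, restrictive 85.6. The gap is 18.8.

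Because the trial sets out to move the two distributions apart, even an identical rule selects different fractions of each arm. The sign of the error depends on where clinicians' attention falls, which is not documented.

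**Day axis.** The SAP does not say whether days count from the bleed, admission or randomization. The mandated window counts from the bleed. In the pilot the median day of randomization was 3 (IQR 2–5; Protocol 8.1). On a randomization axis, the end of mandated sampling would therefore fall on a different plotted day for each patient.

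**The case against.** This is a tertiary outcome shown descriptively, and several things limit the consequence.

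- SAP 5.3 promises missing-data frequencies, so missingness is not hidden. That stands, but it does not commit the plan to counts per arm and day, which a reader of this plot needs.
- Delivery of the strategies is also reported through the proportion transfused, the adjusted median difference in RBC units, and violations per patient (SAP 3.2 and 5.2). That stands too. A null result would not be read from this plot alone, although none of those measures is hemoglobin separation.
- The SAP moved the outcome to tertiary, so the protocol's regression commitment may be regarded as superseded. Even so, the SAP's own objective remains comparative.
- A likelihood-based mixed model assumes missing at random. If sampling depends on a current hemoglobin that nobody measured, the model does not remove the bias. This is correct, and it is why the main summary should stop at day 10.

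Three stronger readings are tempting and the documents do not support them. A reader might infer that the separation will be misread. That is not shown: under some plausible sampling patterns the gap is unbiased, and the days to day 10 are sound. A reader might infer that the plot understates early separation because it uses the daily minimum rather than an average or post-transfusion value. But the minimum is the pre-specified outcome, and a different quantity is not its true value. A reader might also take Protocol 9.1, "We will monitor daily hemoglobin measures to ensure compliance of transfusion within 6-hour target of meeting the threshold", as a promise of daily values throughout. It concerns monitoring of compliance and does not extend the sampling rule.

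**Conclusion.** The point holds in two parts of different strength. That no between-arm estimate is planned for a comparatively worded objective follows from the text alone and needs no assumption. That the separation on days 11–21 may be distorted follows from the sampling rule, but its size and direction cannot be computed from the documents. The illustrations, 12.0 to 18.8 g/L for an assumed true 15 g/L, show only that it could go either way by a few g/L; sampling unrelated to hemoglobin leaves the gap intact. The change is worth making because it lets the SAP answer its own objective, but it is a reporting and estimation matter for a tertiary outcome. The primary analysis, alpha and sample size are unaffected.

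**What to change.** In SAP 5.2 and the matching row of Table 4:

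1. Add a linear mixed model for repeated lowest daily hemoglobin, with treatment, day, treatment-by-day and sex as fixed effects, a random centre effect, and a patient random effect or within-patient covariance. Report the between-arm mean difference with 95% CI and no p-value, in line with SAP 3.1.
2. Make the days to day 10 after the bleed the main summary, since all inpatients on protocol then have mandated sampling. Do not extend it by ICU/HAU stay, which is a post-randomization state.
3. Show days 11–21 separately as descriptive, with a note that the model assumes missing at random.
4. Define the day axis, and say how death, discharge and unsampled days are treated. Print under the plot, per arm and day, the number in hospital and the number sampled.

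The cost is SAP wording and one extra model on data already collected, with no new blood draws. SAP 2.5 puts publication of the SAP before database lock, so the change belongs before that point.

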- 3 **SAHaRA Canadian multicenter observational study:** We conducted a multicenter retrospective cohort study of aSAH patients (n=527) admitted to any of 4 academic centers across Canada between 1 January 2012 and 31 December 2013. The primary objective was to describe a Canadian aSAH population with respect to both anemia incidence and RBC transfusion practices.^{23,28} Anemia (hemoglobin \leq 100g/L) prevalence was 51.8% and the median pre-transfusion hemoglobin in the 19% of the cohort transfused was 79g/L (IQR: 74-93). (Supported by peer-reviewed grants from Depts of Medicine/Critical Care, uOttawa, presented at an international conference^{23,28})

CIHR/CBS-funded pilot RCT (NCT02483351): We have successfully completed enrolment into the SAHaRA internal pilot RCT, the principal (SE) and SAHaRA investigators, in collaboration with the CCCTG, have demonstrated successful recruitment, adherence to intervention, and trial protocol feasibility. There have been 2 interim analyses and DSMB reviews which supported continuation without modification (60 of 60 patients), we demonstrated a recruitment rate of >1 patients/center/month. Adherence to treatment allocation was 92% (15 deviations and 3 violations from 97 transfusion episodes). The difference of mean pre-transfusion hemoglobin between groups was 21.1 ± 6.5 g/L. RBC transfusion occurred within 6 hours of trigger hemoglobin in 84.5% of transfusions and within 11 hours in 100%. We have created the necessary infrastructure, procedures and network to successfully conduct the full trial. (Funded CIHR/CBS-201507-SE-343843; Protocol manuscript published²⁹)

With this above work, the network-building and partner collaborations we have established, we are perfectly positioned to complete the SAHaRA trial.

6 Approach and Methods

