2.2 Randomization

A web-based central computer-generated randomization, stratified by centre, was undertaken from the sponsoring centre. Upon meeting the randomization criteria, patients were randomized in a 1:1 manner to either restrictive or liberal RBC transfusion strategy groups, stratified by site. Variable random blocks of 4 and 6 was used. For patients randomized to the restrictive group, an RBC transfusion is permitted once a hemoglobin level of ≤ 80 g/L is observed over the first 21 days following aSAH. For patients randomized to the liberal group, an RBC transfusion is permitted once a hemoglobin level of ≤ 100 g/L is observed over the first 21 days in hospital following aSAH. The trial is an open-label blinded-endpoint randomized control trial. All outcomes are ascertained by an assessor (trained and qualified study personnel) blinded to the intervention and who has had no part in the management of the patients.

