2.3 Sample Size

Based on our foundation work and previously published literature, we anticipate unfavourable neurologic outcome (mRS score of ≥ 4) at 12 months in 40% of the restrictive arm group.^{8,11,15,16} Previous studies involving SAH patient populations have supported a minimal clinically important difference (MCID) of a 25% relative improvement in poor neurologic outcome.¹⁷ Therefore, to demonstrate a 25% relative improvement in event rate (i.e., from 40% to 30%), a total sample size of 740 patients (test of independent proportions¹⁸) is necessary given 80% power, a type I error of 5% and a conservative 3% loss to follow-up factor.

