3.1 Confidence Intervals and P-values

The statistical uncertainty of all estimates will be expressed as two-sided 95% confidence intervals. Therefore, the analyses for an unfavorable neurologic outcome will be tested at a 0.05 level of significance. A p-value will only be reported for the primary outcome.

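### The log-binomial mixed model planned for the proportion transfused is poorly suited to a liberal arm that the design pushes towards 100%, and the SAP names no fallback

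*SAP*

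**What the plan says.** **Proportion transfused.** SAP 5.2 (Tertiary Outcomes) plans "Proportion of patients receiving RBC transfusion with between group differences analysed using using a log-binomial GLMM". The opening of 5.2 and Table 4 make this a model with treatment and sex as fixed effects and centre as a random effect. Table 4 adds an unadjusted version.

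**Design.** SAP 4.1 requires Hb ≤100 g/L at entry. SAP 2.1 sets the liberal trigger at the same value and states: "Transfusion in this arm is mandatory". In the restrictive arm, transfusion at ≤80 g/L is allowed but left to usual care. SAP 2.2 describes the liberal trigger as allowing transfusion, which does not match 2.1, and the two should be reconciled. SAP 3.2 counts an untransfused liberal crossing as non-adherence. Protocol 9.1 also lets a repeat Hb above the trigger close the event.

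**Transfusion-related adverse events.** SAP 5.1 lists these as one outcome, and 5.2 models the proportion of patients affected, again log-binomially. Protocol 10.2.1 gives only upper bounds: two reactions below 1%, five below 0.1% and three below 0.001%. It does not say whether the denominator is patients or transfusions. Table 4 gives a median and IQR as the additional analysis for this yes/no outcome.

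**RBC units.** "Median number of RBC units transfused will be reported with interquartile ranges and presented as median difference with 95% CI using quantile regression", adjusted for site and sex.

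**Precision.** SAP 3.1 wants the uncertainty of all estimates "expressed as two-sided 95% confidence intervals". Neither document says what to do about non-convergence, a fitted risk of 1 or more, an arm with no events, or heavily tied counts.

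**The concern.** A log link does not keep fitted risks below 1. That is harmless when both arms have moderate risks, but here one arm is meant to sit close to 1. A normal centre effect on the log scale makes it worse, because it has no upper limit and the same centre variance is imposed on both arms. The software can then stop without a solution, or shrink the centre variance to almost nothing and report standard errors that do not match the true spread.

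The proportion transfused is direct evidence that the two strategies differed in practice, and readers of a transfusion-threshold trial will look for it. If the stated model does not fit, the analyst has to choose another after seeing the data.

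**Working it through.** **1. Arm size.** SAP 2.3 gives 740 patients, which "is necessary given 80% power, a type I error of 5% and a conservative 3% loss to follow-up factor", for 40% versus 30%. SAP 2.2 gives 1:1 allocation. With no continuity correction:

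n = [1.96·√(2·0.35·0.65) + 0.842·√(0.40·0.60 + 0.30·0.70)]² / 0.10² = 356 per arm, 712 in total.

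356/0.97 rounds up to 368 per arm, 736 in total, so 740 is reproduced to within 1%. I use 370 per arm.

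**2. Room below a risk of 1.** At liberal risk p, the centre effect can rise by −ln(p) before the fitted risk reaches 1. For a normal centre effect with log-scale SD 0.1 (assumed), the share of centres above 1 is 1 − Φ(−ln(p)/0.1).

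| Liberal risk | −ln(p) | Share above 1 |
|---|---|---|
| 40% | 0.916 | 0% |
| 90% | 0.105 | 15% |
| 95% | 0.051 | 30% |
| 98% | 0.020 | 42% |
| 99.5% | 0.005 | 48% |

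**3. Simulated fits of the planned mixed model.** The first fit assumed 35% transfused in the restrictive arm, 20 centres, 80% female and a centre SD of 0.4 on the logit scale, with 150 runs per setting. The second was a separate fit of the same type of model. SAS, the SAP's software, was not available for either.

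| Liberal rate | Converged, first fit | Converged, second fit |
|---|---|---|
| Reference: arms at 40% and 30% | 98% | 80% |
| 90% | 58% | 65% |
| 95% | 37% | 40% |
| 98% | 23% | 38% |
| 99.5% | 5% | 20% |

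- At 98% and above, the first fit's median model SE was about 0.80 against an empirical SD of 0.085 to 0.09, which is far too large. The second fit's SE was 0.07 to 0.08 against 0.12 to 0.16, which is too small. The errors run in opposite directions, but neither SE is usable.
- In the first fit the estimated centre SD fell from 0.226 at the reference to 0.019 at 95% and 0.009 at 98%, although the simulated centre variation was unchanged.
- Point estimates held up: risk ratio 2.72 against a true 2.80 at 98%.
- Dropping the centre effect is not a full cure. Fitted risks of 1 or more still appeared in 2.5%, 20.5% and 75% of runs at 95%, 98% and 99.5%.
- The chance that all 370 liberal patients are transfused is 0.98^370 = 0.0006, 0.99^370 = 0.024 or 0.995^370 = 0.157.

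**4. Transfusion-related events.** Assume liberal rate r and restrictive rate 0.367r (the exposure ratio from step 5). The chance of at least one empty arm is 1 − [1 − (1−r)^370]·[1 − (1−0.367r)^370].

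- Any listed reaction: the upper bounds sum to 2·1% + 5·0.1% + 3·0.001% ≈ 2.5%. Expected events are 9.3 and 3.4, and the chance is 0.03 (0.01 to 0.16 for an exposure ratio of 50% to 20%).
- One reaction at 1%: 3.7 and 1.4 events, chance 0.27 (0.18 to 0.49 over the same range).
- One reaction at 0.1%: 0.37 and 0.14 events, chance 0.96.

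In a simulated dataset with no restrictive events, the log risk ratio came out at 20.3 with SE 16,311, so there was no finite estimate.

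**5. RBC units.** Protocol 5.3 reports that anemia prevalence was 51.8% and that "the median pre-transfusion hemoglobin in the 19% of the cohort transfused was 79g/L". If every transfused patient was anemic, at most 0.19/0.518 = 36.7% of anemic patients were transfused. That leaves at least 63.3% untransfused and a median of 0 under that practice.

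Simulated median regressions assumed 1+Poisson(1.3) units in the liberal arm and 1+Poisson(0.6) in transfused restrictive patients:

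- At 63% untransfused, the difference was estimated correctly (2.0 in 12 of 12 datasets), although bootstrap intervals had zero width in all 12.
- Interval coverage was 96% to 100% at 40%, 45%, 55% and 63% untransfused, but 53% at exactly 50%.
- At 45% untransfused, with site and sex in the model and a true difference of 1, the estimate was 1 in nine datasets and 2 in three.
- A mean-difference interval covered 94% to 96% throughout.

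**6. An alternative that fits.** Modified Poisson gave an estimate in all 200 runs at each setting. Risk ratios were 2.67, 2.79, 2.79 and 2.83 at liberal rates of 95%, 98%, 99.5% and 100% against 35%. Its robust SE was about 0.07 against an empirical SD of 0.085 to 0.10, in a version that ignored centre.

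**The case against.** The documents give no liberal-arm rate, and 100% is not guaranteed. A repeat Hb can close a threshold event under Protocol 9.1, and SAP 3.2 treats a missed transfusion at 95 to 100 g/L as only a deviation. Convergence rates from non-SAS code need not carry over, and the second fit converged in only 80% of runs even at moderate risks. Point estimates stayed close. The outcome is tertiary, only the primary outcome has a p-value, and separation is also shown by the daily hemoglobin graph and the adherence counts.

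All of this stands, and it limits the size of the point. It does not remove it. The model already struggled at 90% to 95%, the intervals are what SAP 3.1 asks for, and no substitute is named.

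A reader might go further and infer that all three tertiary models will fail. The documents do not support that:

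- **Adverse events.** The planned outcome is patients with any transfusion-related event, not a model for each reaction, and such a composite seldom leaves an empty arm. Expected adverse events, named in the same SAP line, have no stated rate and need not be rare.
- **RBC units.** A restrictive median of 0 is inferred from a retrospective usual-care cohort; the design does not force it. If it occurs, the median difference remains a valid quantity and is estimated correctly. Coverage failed only when almost exactly half of that arm was untransfused, so quantile-regression intervals are not invalid in general.

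**Conclusion.** The point holds for the proportion transfused. The model does not suit the design: it is likely not to converge, or to give intervals that cannot be trusted, once the liberal rate is high. Simulated convergence was 37% to 40% at a 95% liberal rate and 5% to 20% at 99.5%. These figures rest on an assumed liberal rate and on software other than SAS; the first fit also assumed 35% transfused in the restrictive arm and particular centre variation. Failure is therefore a substantial risk, not a certainty.

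For transfusion-related events the problem is confined to single reaction types or an arm that happens to be empty. For RBC units it is confined to instability when about half of the restrictive arm is untransfused. No primary or secondary conclusion is affected. The change is still worth making, because it costs little and removes a choice that would otherwise be made after seeing the data.

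**What to change.** In SAP 5.2 and Table 4, before database lock:

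- **Proportion transfused.** Replace the log-binomial mixed model with one of: a centre-stratified Mantel-Haenszel risk difference; a standardised risk difference from a logistic model; or modified Poisson with robust SE. Modified Poisson keeps the planned risk ratio and the adjustment for centre and sex. If it is chosen, include centre and cluster the robust SE on it, since the version that ignored centre understated the spread. Mantel-Haenszel stratified by centre alone gives up the sex adjustment.
- **Transfusion-related adverse events.** Report counts with an exact interval for the risk difference whenever an arm has no events or individual reaction types are compared. Correct the Table 4 entry that gives a median and IQR for this outcome.
- **RBC units.** Keep the median and IQR, and add mean units per randomised patient with a mean difference and a robust or bootstrap 95% CI.

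The cost is a few lines of SAP text and a little more analysis, with no new data. If risk differences are used, these outcomes will be on a different scale from the other binary outcomes.
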